6.1.2 ADMINISTRATION

As stated above, the care coordinators will meet with patients individually for at least 13 visits over six months. In the first two months, the Care Coordinator

CC-COD+ component	CC-COD+ Activities	Length of time
(1) Overdose/suicide risk education	Educate and explore questions about MOUD with SPs Educate SPs about addiction Assess overdose risk and discuss with patient Conduct lethal means counseling with patient	One individual 30-minute session with an SP 18+ nominated by the patient. If the patient wants to nominate more than one adult SP, two can attend this session. Overdose risk and lethal means counseling with the patient will be integrated into the patient’s care initiation visit with the care coordinator.
(2) Naloxone training	Educate patients and SPs on signs of overdose and the importance of naloxone Train patients and SPs on use of naloxone	15 minutes (SPs will receive in their session; patients will receive in their care initiation session)
(3) Caring Contacts	Convey concern/compassion via mailed cards Sent to patient weekly/monthly (titrated over six months) and on patient’s birthday	Ongoing mailed contacts to patients

will meet weekly with the patient. In month three, they will meet biweekly. In months four through six, they will meet with patients once a month. Visits can be in-person or by phone. Care coordinators will be community health workers compared to nurses or behavioral health providers in more traditional

collaborative care studies to address the provider shortage in New Mexico and to increase patient buy-in with a peer delivering the intervention. Each patient participant will be assigned one Care Coordinator to interact with during the six-month intervention period. Participants are not expected to interact with other participants in the intervention. Intervention dose will be measured by the number of visits each patient has with the Care Coordinator and these data will be gathered in the clinical registry.

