could have a time-varying interaction with the intervention or because the most current information is needed for records retrieval (e.g. National Death Index). Exploratory moderator variables include demographic characteristics (i.e., sex and ethnicity); trauma/interpersonal violence, measured using the PTSD checklist for DSM-5, description of worst event; pain levels, measured for the past week using the PEG Pain Monitor;¹⁵ housing status, measured using the Homelessness Screening Clinical Reminder Tool;¹⁶ disability and impairment, measured using the three-item Sheehan Disability Scale;¹⁹ stimulant use frequency, measured using days of stimulant use in the past 30 days from NSDUH⁶ items; and number of care coordinator visits, based on registry entries made by care coordinators.

During follow-up assessments, we will measure key care processes thought to mediate the effects of CC-COD/CC-COD+ on patient outcomes. Specifically, we will examine potential changes in (1) clinician communication, (2) ability to quickly access treatment, and (3) satisfaction with treatment, all using AHRQ Consumer Assessment of Healthcare Providers and Systems survey items,²¹ as well as (4) patient and Care Coordinator working alliance using a modified Working Alliance Inventory.²² Potential mediation will be included in exploratory analyses.

Finally, we have several potential exploratory outcomes: drug use frequency, measured as days of use in the past 30 days for five drug categories (prescription opioids, heroin, cocaine/crack, methamphetamine/ other stimulants, and tranquilizers/sedatives) using SAMHSA National Survey on Drug Use and Health (NSDUH)⁶ items; stimulant use frequency, measured as days of stimulant use (cocaine/crack, methamphetamine/ other stimulants) in the past 30 days from NSDUH;⁶ alcohol use, measured using the 3-item Alcohol Use Disorder Identification Test – Consumption (AUDIT-C)⁸ for the previous 3 months; opioid overdose risk behaviors, measured with the Opioid Overdose Risk Assessment;⁹ and opioid use severity, measured using the 7-item Patient-Reported Outcomes Measurement Information System (PROMIS) Substance Use Short Form⁷ for the previous 30 days.

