barriers to care, provides information about treatment options, and then coordinates next steps with the patient. After the care initiation visit, the Care Coordinators meets with the patient in monitoring visits for the remainder of the six-month intervention period. Care monitoring visits focus on engagement, assessment, and linkages. Five opioid use questions are asked at each visit, whereas the PROMIS-7, PCL-5, and PHQ-9 are administered monthly. In this care model, the Care Coordinator is supported by a behavioral health consultant (BHC) and a Care Coordinator supervisor with expertise in supervising community health workers. The Care Coordinator, BHC, and Care Coordinator supervisor meet weekly to discuss the Care Coordinator's caseload. Throughout the study period, the Care Coordinator enters patient information into a clinical registry, a patient caseload tool with four main purposes: (1) track population-level outcomes and engagement, (2) prompt the Care Coordinator with reminders and alerts to ensure accountable outreach when a patient has an upcoming appointment or needs a higher-level of care, (3) prompt treatment-to-target by showing trends in patient symptom severity scores and flags the Care Coordinator when to consult with the BHC, and (4) facilitate caseload review between the Care Coordinator, BHC, and Care Coordinator supervisor through caseload-level reports that display patient-level ID numbers of those who should be discussed.

Enhanced Usual Care (EUC) intervention. EUC includes both the evidenced-based psychotherapy (i.e., Problem Solving Therapy for depression and Written Exposure Therapy for PTSD) and pharmacotherapy (i.e., MOUD and psychotropic medications for MDD/PTSD) provided in CC-COD, but the primary difference is the absence of a care management team and a clinical registry to coordinate care with the patients in EUC.

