2.5.4 Other measures

Table 4 provides the definition of additional measures that will be used as potential mediators and moderators in exploratory analyses described below.

Table 4: Definition of additional potential mediation and moderation variables

Measure	Instrument	Measure Scale	Source
Potential Moderators			
Trauma/Interpersonal Violence	PTSD Checklist for DSM-5, description of worst event	Categorical*	Survey
Sex	Sex on current birth certificate	Categorical**	Survey
Ethnicity	Patient-reported ethnicity	Binary (Hispanic/non-Hispanic)	Survey
Pain	PEG Pain Monitor, for past week	Mean of 3 items (0-10)	Survey
Disability and impairment	Sheehan Disability Scale	Sum of 3 items (0-30)	Survey
Stimulant use frequency	Days of stimulant use (cocaine/crack, methamphetamine/ other stimulants) in the past 30 days from NSDUH	Total days of use (0-30)	Survey
Housing status	Homelessness Screening Clinical Reminder	Categorical***	Survey
Number of care coordinator visits	Care coordinator entry of visits with patient	Continuous	Registry
Potential Mediators			
Clinician communication	CAHPS ECHO	0-100	Survey
Ability to quickly access treatment	CAHPS ECHO	0-100	Survey
Overall rating of treatment	CAHPS ECHO	0-100	Survey
Patient and care coordinator working alliance	Working Alliance Inventory	Mean of 12 items (min=1, max=5)	Survey

*no trauma, trauma w/o IPV, trauma w/ IPV; **male, female, gender neutral; ***stably housed, unstably housed, unhoused

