3.4.6 Moderation analyses

All analyses of subgroups are considered exploratory. We will explore the data to understand if any of the following baseline factors moderate the effect of the intervention:

- Sex
- Ethnicity
- Stimulant use (methamphetamine or cocaine use)
- Housing status
- History of trauma/interpersonal violence

- Pain (PEG)
- Disability and impairment (SDS)
- Number of care coordinator visits

Definitions for these moderation variables are described in Table 4. Additional moderators may be explored as warranted. Statistical hypotheses testing whether the effect of the intervention varies by these factors will be tested by the inclusion of an interaction between the moderating factor and the treatment assignment into the previously described models. We will also utilize propensity score weighting if deemed necessary here to correct for potential imbalances between the treatment groups within levels of the moderators.⁵

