3.4.7 Mediation analyses

We will assess several potential mediators in this study, including whether patient experiences of care and working alliance with the care coordinator at 3 months mediate the impact of CC-COD on patient. Specifically, we consider the following mediators:

1. clinician communication,
2. ability to quickly access treatment,
3. overall rating of treatment, and
4. patient Care Coordinator working alliance using a modified Working Alliance Inventory.

To ensure a proper temporal ordering of the treatment, mediators, and outcomes, all outcomes for the mediation analyses will be measured at 6-months, while the mediators will be measured at the 3-month follow-up.

All mediation analyses will follow the approach described in Imai, et al. (2010),⁶ including the technical assumptions necessary to identify causal mediation effects. This methodology requires the specification of a model predicting the mediator using only baseline information, and a model predicting the outcome using both baseline information and the mediator. For a continuous mediator and outcome, the models have the form:

$$\begin{aligned} M_{ij} &= \eta_j + \varphi T_{ij} + X_{ij} \boldsymbol{\omega} + \epsilon_{ij} \\ y_{ij} &= \alpha_j + \beta T_{ij} + \delta M_{ij} + X_{ij} \boldsymbol{\tau} + e_{ij}, \end{aligned}$$

where $\varphi * \delta$ represents the causal mediation effect under necessary technical assumptions. For binary outcomes or mediators, the models will be specified as logistic regression models. We will use the *mediation* package for the R computing environment to conduct these analyses.⁷

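### Care-coordinator visits cannot be tested as a baseline moderator, and 3-month mediators do not precede buprenorphine continuity, which is counted from enrolment

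*SAP*

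**What the plan says.** **Moderation.** SAP 3.4.6 introduces eight candidate moderators with the words "We will explore the data to understand if any of the following baseline factors moderate the effect of the intervention". The last of them is "Number of care coordinator visits". Each hypothesis "will be tested by the inclusion of an interaction between the moderating factor and the treatment assignment into the previously described models". SAP Table 4 (section 2.5.4) gives the instrument as "Care coordinator entry of visits with patient" and the source as the registry; Protocol 8.1 agrees ("number of care coordinator visits, based on registry entries made by care coordinators"). Protocol 6.1.2 measures intervention dose by "the number of visits each patient has with the Care Coordinator and these data will be gathered in the clinical registry". On the control arm, SAP 2.3 says "the primary difference is the absence of a care management team and a clinical registry to coordinate care with the patients in EUC".

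**Mediation.** SAP 3.4.7 takes mediators at 3 months and every outcome at 6 months, giving the reason "To ensure a proper temporal ordering of the treatment, mediators, and outcomes". It does not name the outcomes; the sentence that should do so stops short. The mediator row of the Protocol Section 3 table names four: buprenorphine access, buprenorphine continuity, and PHQ-9 and PCL-5 at 6 months. SAP 2.1.2 confines mediation to quality of treatment and to what patients report. Continuity falls under the first, because Protocol 4.1 names MOUD continuity as the measure of OUD care quality. In Protocol Section 3 and SAP Table 1, continuity is the cumulative count of buprenorphine days over the 180 days from enrolment.

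**The concern.** A moderator has to exist in both arms and should not be a consequence of assignment. Coordinator visits fail on both counts: they are part of the intervention being delivered, and the control arm has no registry in which to record them. The stated interaction model would then either fail or, if the software drops a redundant column, return a non-randomised dose-response within the intervention arm under the label of moderation.

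A mediator has to come before the outcome it is said to explain. Continuity starts to accumulate on the day of enrolment, so part of it is already fixed when the mediator is asked about. A patient who has been on buprenorphine for two months may rate care or the working alliance more highly because of that treatment. The SAP models adjust only for baseline information, so this reverse path would be read as mediation while the plan states that order is assured.

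The stakes are limited to exploratory results. Mediation is, however, also Hypothesis 2 (Protocol 1.1) and a secondary objective, so its results are likely to be reported.

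**Working it through.** The plan states no figure on this point, so there is none to reproduce. The checks use its definitions and its observed summaries.

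**1. Timing of visits.** SAP 2.3 schedules weekly visits in months 1-2, fortnightly in month 3 and monthly in months 4-6: about 8 + 2 + 3 = 13, all after randomisation.

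**2. Can the interaction be estimated?** Let T be arm (1 = intervention) and V the registry visit count. The model columns are 1, T, V and T×V.

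- EUC visits coded 0: V = 0 whenever T = 0, so T×V = V for every patient. Rank is 3 of 4.
- EUC visits missing: only T = 1 remains, so T equals the intercept and T×V = V. Rank is 2 of 4.
- With four health-system effects and prior MOUD, as in SAP 3.4.4, there are 8 columns. Rank is 7 in the first case and 6 in the second.

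A numerical check on 400 simulated patients (intervention visits Poisson with assumed mean 6) gave these ranks. The result does not depend on the distribution chosen.

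**3. Calendar share of continuity before the mediator.** Protocol 1.3 places the 3-month interview at day 90, -14/+30, which is days 76-120. Protocol 8.1 gives -2/+4 weeks, which is days 76-118.

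- 76/180 = 42%
- 118/180 = 66%
- 120/180 = 67%

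**4. Counted days before the mediator.** SAP 3.5.1 reports a mean of 133.0 days among initiators. At most 180 - d of those days can fall after day d, so the mean accumulated by day d is at least 133.0 - (180 - d), whatever the pattern of use.

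| Interview day d | Minimum mean days already counted | Share of 133.0 |
|---|---|---|
| 76 | 133 - 104 = 29 | 22% |
| 90 | 133 - 90 = 43 | 32% |
| 118 | 133 - 62 = 71 | 53% |
| 120 | 133 - 60 = 73 | 55% |

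Patients with no buprenorphine days add nothing before or after day d, so the same minimum shares hold when they are included. SAP 3.5.1 describes the 133.0 as continuous days; if the cumulative mean is higher, the shares rise.

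**5. Access.** SAP 3.5.1 gives mean 26.0 and SD 31.9 days. Cantelli's inequality puts the share before day d at no less than 1 - SD²/(SD² + (d - mean)²). At d = 76 this is 1 - 31.9²/(31.9² + 50²) = 1 - 1017.6/3517.6 = 71%. So at least 71% of the summarised access times come before the earliest mediator interview. The SAP does not say whether that mean covers initiators only.

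**The case against.** The strongest reply is about weight. SAP 3.4.6 labels all subgroup work exploratory, Protocol 4.1 and 8.1 say the same of mediation, visits are one entry in eight, and an analyst would notice the aliasing at once. This stands as a limit on importance, but it does not make the stated analysis possible.

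Second, Protocol 4.1 concedes that contamination may occur, and Protocol 4.2 says some clinics already have coordinators whom EUC patients may see. Any non-zero EUC counts would restore full rank. That is true in algebra, but the moderator is defined by study-registry entries, and neither passage describes a route by which an EUC patient acquires them. Stray entries would leave the interaction resting on those few patients and on a variable that is still post-randomisation. The optional propensity weighting in SAP 3.4.6 cannot supply EUC patients with visits.

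Third, the baseline label is the SAP's alone: Protocol 8.1 allows some moderators to be measured at follow-up. This is correct, and it means that the two documents differ. It does not rescue the interaction.

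Fourth, SAP 3.4.7 makes causal reading conditional on technical assumptions. Those concern identification; they do not put days already counted after the interview.

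Fifth, SAP 3.5.1 words the 133.0 figure in terms of OUD medication in general. If it included other medication, the counted-day bounds would be lower. SAP 1.2 largely answers this: continuity was made buprenorphine-specific and power was recalculated with the modified outcomes. The calendar shares do not depend on it.

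**Conclusion.** Both items are wrong as written.

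- **Visits.** The arm-by-visits interaction cannot be estimated, given that EUC patients have registry counts of zero or none.
- **Temporal order.** The claim holds for 6-month PHQ-9 and PCL-5 but fails for buprenorphine continuity. Between 42% and 67% of the counting window precedes the interview, and at least 22% to 55% of counted days do so if the 133.0 mean is a buprenorphine mean. That continuity is a mediated outcome rests on the Protocol Section 3 table and on reading SAP 2.1.2 with Protocol 4.1, because SAP 3.4.7 does not list its outcomes.

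Access is a matter for reconciliation: only Protocol Section 3 lists it as a mediated outcome, and SAP 3.4.7 gives no time-to-event mediation model. Two further points need clarification only. The SAP has no rule for working alliance in EUC patients without a coordinator. The communication mediator refers to the care coordinator in Protocol 1.3 but to the clinician in Protocol Section 3, Protocol 8.1 and the SAP.

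The four primary tests and their power figures are unaffected.

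**What to change.** 1. Delete the coordinator-visit count from the moderator lists in SAP 3.4.6, SAP Table 4, Protocol Section 3 and Protocol 8.1. If it is wanted, report it as a non-randomised description of dose within the intervention arm.
2. In SAP 3.4.7, name the mediated outcomes. For continuity, either count buprenorphine days for the mediation analysis only in a fixed window after the 3-month survey closes (for example days 121-180, which clears both stated interview windows), or withdraw the ordering claim for that outcome. In either case, state that earlier buprenorphine use remains a post-randomisation confounder of mediator and outcome.
3. Reconcile Protocol Section 3 with SAP 2.1.2 and 3.4.7 by removing access from the mediator row.
4. State which provider the communication items refer to, and how working alliance is handled for EUC patients without a coordinator, before treating either mediator as defined in both arms.

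The cost is wording; existing data suffice. A 60-day window keeps one third of the 180 days, so it carries less information, and it does not remove confounding by earlier use. SAP 2.2 says the plan was finalised before unblinding, so the changes should be dated and labelled as later amendments.

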3.4.7 Mediation analyses

We will assess several potential mediators in this study, including whether patient experiences of care and working alliance with the care coordinator at 3 months mediate the impact of CC-COD on patient. Specifically, we consider the following mediators:

1. clinician communication,
2. ability to quickly access treatment,
3. overall rating of treatment, and
4. patient Care Coordinator working alliance using a modified Working Alliance Inventory.

To ensure a proper temporal ordering of the treatment, mediators, and outcomes, all outcomes for the mediation analyses will be measured at 6-months, while the mediators will be measured at the 3-month follow-up.

All mediation analyses will follow the approach described in Imai, et al. (2010),⁶ including the technical assumptions necessary to identify causal mediation effects. This methodology requires the specification of a model predicting the mediator using only baseline information, and a model predicting the outcome using both baseline information and the mediator. For a continuous mediator and outcome, the models have the form:

$$\begin{aligned} M_{ij} &= \eta_j + \varphi T_{ij} + X_{ij} \boldsymbol{\omega} + \epsilon_{ij} \\ y_{ij} &= \alpha_j + \beta T_{ij} + \delta M_{ij} + X_{ij} \boldsymbol{\tau} + e_{ij}, \end{aligned}$$

where $\varphi * \delta$ represents the causal mediation effect under necessary technical assumptions. For binary outcomes or mediators, the models will be specified as logistic regression models. We will use the *mediation* package for the R computing environment to conduct these analyses.⁷

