1 PROTOCOL SUMMARY

1.1 SYNOPSIS

Title: Improving Access and Treatment for Co-occurring Opioid Use Disorders and Mental Illness

Grant Number: U01 MH 121594

Study Description:

This is a multi-site, randomized pragmatic trial in rural and urban primary care clinics located in New Mexico and California to adapt, harmonize and then test whether CC-COD improves access, quality and outcomes for primary care patients with co-morbid OUD and depression and/or PTSD. We will randomize patients with co-occurring OUD and depression and/or PTSD to receive either CC-COD or enhanced usual care (EUC).

Summary of Competitive Revision (CR): The CR develops and then tests an enhanced version of the parent study's collaborative care intervention for co-occurring disorders (CC-COD) to reduce the risk of suicide and opioid-related overdose among individuals with opioid use disorder (OUD) in combination with PTSD/depression. Within each clinic, once enrollment into the parent study has been completed (N=900), clinics will transition to delivering CC-COD+ and patients (N=300) will be randomized to either CC-COD+ or EUC. All study procedures and measures are identical for both the parent study and the CR. Because the CR did not enroll sufficient individuals to allow for separate analyses, it was decided to combine patients enrolled into the parent study intervention arm, with patients enrolled into the CLARO+ study intervention arm for all analyses. This was discussed and approved by our Research Advisory Board.

Hypothesis 1: Patients randomly assigned to CC-COD/CC-COD+ will have significantly increased buprenorphine access and quality of care, and depression and PTSD outcomes compared to patients assigned to EUC.

Hypothesis 2: Patient experiences will mediate the effect of CC-COD on quality and outcomes compared to patients assigned to EUC.

Objectives:

Primary Objective: To evaluate the effectiveness of CC-COD/CC-COD+ on patient initiation of MOUD, quality of care for OUD; and depression and PTSD patient outcomes relative to EUC.

Secondary Objectives: To test mediators (patient experiences with care and working alliance with the Care Coordinator) of treatment quality and patient-reported outcomes and, in exploratory analyses, test moderators of access, quality, and outcomes compared with patients assigned to EUC.

Endpoints:

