3.4 Statistical models

3.4.1 Notation

Table 8 provides notation used to describe the statistical models. We note that the sample size per primary care clinic where not large enough to support the use of fixed effects by clinics in our regression models. Instead, we utilize fixed effects for health systems. When the sample sizes for the smallest health systems prove too small (e.g., less than 30 for continuous

outcomes), we will collapse the smallest health systems together for the purposes of our regression models.

Table 8: Notation used to describe the statistical models.

Notation	Description
X_{ij}	The baseline characteristics of participant i at health system j , including both demographics and other baseline characteristics.
P_{ij}	An indicator of prior MOUD treatment for participant i at health system j .
T_{ij}	The random treatment assignment of participant i at health system j .
y_{ij}	An outcome measure for participant i at health system j .
R_{ij}	An indicator denoting whether participant i at health system j responded to the 6-month follow-up survey.
M_{ij}	A mediator of the outcome-treatment relationship for participant i at health system j .

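### Each 3-month care-experience mediator is modelled with the others left out, so an experience with no effect of its own can be credited with mediation if the mediators are correlated

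*SAP*

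**What the plan says.** SAP 3.4.7 introduces its list with "Specifically, we consider the following mediators" and names clinician communication, quick access to treatment, overall rating of treatment, and working alliance with the Care Coordinator. On timing, outcomes are taken at 6 months, "while the mediators will be measured at the 3-month follow-up".

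The method needs two models: one for the mediator from baseline information, and "a model predicting the outcome using both baseline information and the mediator". As written for a continuous outcome, the second contains health-system effects, treatment, one term delta·M_ij and X_ij·tau. The product phi·delta "represents the causal mediation effect under necessary technical assumptions". Table 8 in SAP 3.4.1 defines M_ij in the singular ("A mediator of the outcome-treatment relationship for participant") and X_ij as baseline characteristics, "including both demographics and other baseline characteristics".

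Hypothesis 2 in the protocol synopsis reads: "Patient experiences will mediate the effect of CC-COD on quality and outcomes compared to patients assigned to EUC". The synopsis and SAP 2.1.2 make testing mediators a secondary objective. The objectives table in protocol section 3 puts it under tertiary/exploratory, and protocol 8.1 says "Potential mediation will be included in exploratory analyses".

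Neither document gives a model with several mediators, a sensitivity analysis for correlated mediators, or a multiplicity rule for mediation.

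**The concern.** For phi·delta from a one-mediator model to be that mediator's causal indirect effect, no other variable affected by treatment may influence both the mediator and the outcome. The SAP's list names three other variables that it thinks may be moved by treatment and may affect the outcome. All four are reports by the same patient at the same follow-up, so correlation is plausible. Where it exists beyond treatment and X, each delta absorbs part of the effect of the omitted mediators. The SAP mentions the technical assumptions but plans no check of them.

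What is at stake is the item-level reading. Someone wanting to know which part of the care experience to strengthen could be shown several mediators when only one is active. This is bias, so a larger sample does not remove it.

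**Working it through.** **The plan's own figures.** The SAP states no power, error rate or sample size for mediation, so there is nothing on this point to reproduce. As an anchor for the sample sizes, the detectable differences in SAP 3.5.1 were recomputed at two-sided alpha 0.0125. Power is 0.803 (18.3 days, SD 54.1, N = 392), 0.804 (2.2 points, SD 6.6, N = 405) and 0.805 (6.23 points, SD 17.8, N = 368), against the stated 80%.

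**Assumed inputs.** The documents give none of these: pairwise residual correlation rho between mediators; an arm effect of phi SD on each; one active mediator with effect delta SD per SD; a 95% interval for phi·delta; no baseline covariates.

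**Size of the bias.** If only M1 affects the outcome, regressing y on T and M2 alone gives M2 a coefficient of rho·delta. Its apparent indirect effect is then phi·rho·delta, which is rho times the true phi·delta. With phi = delta = 0.3 the true effect is 0.090 SD. The inert mediator is credited with 0.3 × 0.090 = 0.027, 0.5 × 0.090 = 0.045 and 0.7 × 0.090 = 0.063. Simulation at N = 405 gave 0.027, 0.044 and 0.063.

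**How often an inert mediator is declared.** Four mediators, phi = delta = 0.3, 1,500 simulated trials per setting:

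| rho | One at a time, N = 405 | One at a time, N = 368 | At least one of three inert, N = 405 |
|---|---|---|---|
| 0 | 3.3% | 4.3% | 10.6% |
| 0.3 | 35.7% | 32.2% | 65.7% |
| 0.5 | 70.3% | 66.8% | 91.3% |
| 0.7 | 83.1% | 80.5% | 93.7% |

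With all four in one outcome model, a given inert mediator is declared in 0.2–5.2% of trials over all settings run. Testing one at a time at 1.25% still gives 44.4% at rho = 0.5 and N = 405, so a multiplicity correction does not cure it.

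**Range over the assumptions.** For N = 350–400, phi 0.3–0.5 and delta 0.2–0.3, simulated rates are roughly 13–43% (rho 0.3), 36–83% (0.5) and 57–99% (0.7), against about 3–7% when fitted jointly. A closed-form approximation multiplies the chance that the arm effect on the mediator is significant (SE = 2/√N) by the chance that the mediator coefficient is (SE = √[(1 + delta²(1 − rho²))/N], outcome residual SD 1). At rho = 0.5:

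- Low end, N = 350, phi 0.3, delta 0.2: z = 0.3/0.107 = 2.81 (0.80) and 0.10/0.0542 = 1.84 (0.45). Product 0.36.
- High end, N = 400, phi 0.5, delta 0.3: z = 0.5/0.100 = 5.0 (1.00) and 0.15/0.0517 = 2.90 (0.83). Product 0.83.

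The same formula gives 0.16–0.41 at rho 0.3 and 0.59–0.98 at rho 0.7, within a few points of the simulation.

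**Where it fades.** With phi = 0 the rate is 4.5% (rho 0.5, N = 405). With phi = 0.1 it is roughly 1–13%; the approximation puts the top corner (N = 400, rho 0.7, delta 0.3) slightly higher, at 0.17 × 0.98 = 0.17.

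**The case against.** Several objections are sound and limit the point.

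- **Hypothesis 2 is about experiences as a group.** In every setting with an inflated rate, one experience really does mediate, so the group conclusion is right. A reader might infer that the plan would accept Hypothesis 2 falsely. The working does not show that: with no arm effect on the mediators, the rate stays near 5%.
- **Overstated total.** A reader might add the separate effects. With three equally shifted mediators and one active, the sum is 1 + 2·rho times the true total: 1.6, 2.0 and 2.4 at rho 0.3, 0.5 and 0.7. But the SAP nowhere sums them or reports mediated shares, so this is a caution for reporting, not an error in the plan.
- **The inputs are assumed and could be smaller.** With phi = 0.2, delta = 0.1–0.2 and N = 300–375, the rates are 2.5–9%, 4–21% and 8–36% at the three correlations. The Ns of 405 and 368 are 6-month respondents; mediation also needs 3-month data, and the overlap is not stated. Baseline covariates could lower rho.
- **One experience may cause another.** Suppose communication drives the overall rating, which drives the outcome (N = 375, arm effect 0.4, paths 0.6 and 0.3; true indirect effect 0.4 × 0.6 × 0.3 = 0.072). The single-mediator model then recovers 0.073 and detects it in 90% of trials, while communication's own term in the joint model averages 0.000 and is detected in 4.5%. Item-level joint coefficients are therefore not a safe replacement. The joint total is unaffected by the order among mediators.
- **Mediation is largely labelled exploratory**, and the SAP conditions its causal reading on assumptions. This lowers the severity, but naming the assumptions does not make them hold.

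The SAP also never says in words that mediators are taken one at a time; this follows from its equation and Table 8.

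**Conclusion.** The point stands in conditional form. As specified, the analysis cannot separate one care experience from another, and an inert one can be declared a mediator. This requires residual correlation among the mediators and an arm effect on the inert one. Both are plausible, but neither is documented, so the rates above show what could happen and do not predict this trial's results.

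The documents do not support saying that an inert mediator will be declared, that Hypothesis 2 is compromised as a group claim, or that any primary comparison is affected. The change is worth making because mediation is a stated secondary objective with its own hypothesis and the remedy needs no new data. It is a should-fix item.

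**What to change.** In SAP 3.4.7:

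1. For continuous outcomes, add one outcome model with all patient-experience mediators together, y = alpha_j + beta·T + Σ delta_k·M_k + X·tau + e. Include working alliance only if it is retained as a mediator. Make the joint indirect effect, Σ phi_k·delta_k with a bootstrap interval, the test of Hypothesis 2.
2. For binary outcomes and for buprenorphine access (time-to-event, analysed by Cox model, N = 137 in SAP 3.5.1), define the joint indirect effect by an analogous counterfactual or simulation-based contrast. The product formula does not carry over.
3. Report single-mediator effects as descriptive, stating that they are neither separable nor additive. Report individual delta_k from the joint model as descriptive too, stating that they exclude any path through another mediator.
4. State one status for the mediation analysis, since the documents call it both secondary and exploratory.

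The cost is SAP wording and one extra model per outcome, with somewhat more specification work for the non-continuous outcomes. Item-level coefficients will be less precise when the mediators are collinear.
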